### Procedure.

After meeting inclusion criteria for the study, she will be given screening tools (General Anxiety Scale – GAD-7, Perceived Stress Scale – PSS, and the Edinburgh Postnatal Depression Scale – EPDS) to determine study participation.

If a potential participant scores:

- Greater than or equal to 10 on the General Anxiety Disorder 7-item scale (GAD-7)
- Or greater than or equal to 20 on the Perceived Stress Scale (PSS)
- Or a cut-off score of 10 on the Edinburgh Postnatal Depression Scale (EPDS)

They will be eligible to participate in the study. For the GAD-7 a score of  $\geq$  to 10 indicates moderate anxiety and maximizes sensitivity and specificity, for the PSS, a score of 20 or greater is the high-stress cut-off and a cut-off score of 10 on the EPDS is suggested to indicate moderate depressive symptoms in pregnant women.

If a **participant does not screen** into the study, she will be thanked for her time and interest and paid \$10.00 for her participation in the screening process.

07/30/2021

If a **participant does screen into the study**, she will provide further baseline data at this point which includes: demographic and personal information, weight from clinic scale, a 24 hour diet recall, the Healthy Lifestyle Beliefs Scale and the Healthy Lifestyle Behaviors Scale.

A participant will then be assigned to the next available group based on fetal gestational age (groups having been scheduled and previously randomized as intervention or control as described above). Participants will then be given an appointment for their first group prenatal care session and a Fitbit Flex 2, with instructions on how to immediately begin using the Fitbit (to provide baseline data that will be uploaded at the first group session) and a Fitbit number (for confidentiality) so that they can compare with other pregnant women. All participants will receive \$30.00 for at the baseline visit, **T0**.

All women in this study will receive 6 sessions of group prenatal care beginning at 16 weeks gestation ( $\pm 2$  week) and ending at 31 weeks ( $\pm 2$  week) according to previously described randomization into COPE-P intervention group or PregnancyPlus attention control group. In the event that group prenatal care is not feasible, the group sessions can be conducted as virtual visits (using programs such as Zoom, WebEx, Facetime etc.) or content can be provided in a 1:1 patient to provider setting. Different care providers will deliver the COPE-P and PregnancyPlus content, assuring that there is no carryover effect of the intervention into the control group. [name] will conduct the training of the attention control group midwives and [name] will conduct the training of the intervention group midwives. The same protocol for assessing fidelity will be used for COPE-P and PregnancyPlus. [name] will train the research team to assess fidelity of the intervention with the intervention fidelity checklist. Fidelity will be assessed by having research team members observe 2 of the 6 sessions for each intervention group. Inter-rater reliability of 90% will be established and observer drift monitored and corrected throughout the trial. Feedback will be provided immediately after the session to interventionists if they are not adhering to the intervention as intended to be delivered.

At the end of the 18-week timeframe and at their last group prenatal care session, all women will complete the GAD-7, PSS, EPDS, a 24 hour diet recall, the Healthy Lifestyle Behaviors Scale and the Healthy Lifestyle Beliefs Scale. Fitbit data and weight also will be obtained. In the intervention group, participants also will complete the COPE-P evaluation. This data will be **T1**, and will be collected at approximately 31 weeks gestational age. For women who miss this visit, data will be collected at the next scheduled prenatal visit. Participants will be compensated \$30 for their study participation.

Data collection at the 3 month post intervention follow up visit, **T2**, will occur at the normally scheduled 4-6 weeks regular postpartum visit. Participants will be compensated \$40 for their study participation at this visit. All measures will be collected.

The 8 month post-intervention visit, **T3**, will be the final data collection point and will occur at a routinely scheduled 6 month well baby visit. Participants will receive \$50 for their participation. All measures will be collected.

A research team member will administer the post-intervention follow-up study questionnaires for each data collection point (T0 – T3). It will be noted how many sessions were completed by the participant. Outcome data from charts will be collected by team members blind to group assignment.

### **Analysis plan.**

**Data management:** Survey data will be obtained using paper and pencil surveys and at each site all surveys will be scanned using Remark software to ensure accuracy and avoid the necessity of double data entry. Fitbit data will be uploaded using Bluetooth technology at each data point (with T0 baseline data being collected between screening and the first group prenatal care session) and entered into an Excel database. Data from the 24 hour diet recalls will be manually entered at each site into Food Processor and then exported into an Excel file for data analyses. At each visit, weights will be recorded. Obstetrical chart data will be extracted at each site. [name] will merge the Ohio and New York data files, perform data cleaning, construct analytic variables, assess psychometrics and conduct both interim and final analyses.

**Data Analysis:** Preliminary analyses: Statistical analyses of these data must not only demonstrate the efficacy

07/30/2021

of the COPE-P intervention, but also map the trajectories of group differences over time, and identify subgroup differences. Analysis will begin with characterization of the sample with descriptive statistics that identify differences between the COPE-P and PregnancyPlus groups 1) evident at baseline, despite randomization and 2) between groups due to differential attrition. Data will be screened for normality, outliers, and homogeneity. Appropriate nonparametric analyses will be considered in situations of irresolvable heterogeneity. We will evaluate the psychometric qualities (reliability, convergent and discriminant validity) of the scales, employing both exploratory factor analyses and SEM measurement models. Descriptive statistics will be used to summarize the sample characteristics and distribution of each variable. Missing Data. All data analyses will be completed as intention to treat analyses (i.e., individuals analyzed by group according to original random assignment, without regard to adherence to the intervention). Missing data will be imputed, when appropriate, using multiple imputation in SAS v9.4 PROC MI.

**Hypothesis-driven analyses.** Various bivariate tests (e.g., independent and dependent t-tests, correlations, ANCOVA and repeated measures analyses of covariance) will be used to evaluate differences and longitudinal patterns of change across time and between relevant subgroups (e.g., intervention groups, language groups) for each significant outcome in the preliminary bivariate analyses, (primary outcomes are healthy lifestyle behaviors, anxiety, stress, and depressive symptoms). For secondary outcomes (appropriate weight gain during pregnancy, birth and post-natal outcomes (e.g., mode of delivery, birth weight/length, gestational age, postpartum weight loss and breastfeeding practices) we will fit a series of longitudinal multilevel growth models to the data.

For all continuous outcomes, such as anxiety, the basic model, to which we can add our controls and predictors. The level 1 submodel estimates how each participant's anxiety changes over the four data collection periods. The level 2 submodel will relate the inter-individual differences to intervention group and other time-invariant predictors and controls, such as medication (i.e., antidepressants) and have begun therapy (i.e., in usual care for mental health diagnoses), and will estimate a participant's initial anxiety level and rate of change in anxiety. Anxiety will be modeled in terms of random subject effects (intercept and time trends) to account for individual differences in how participants change over time. We will begin with a linear model for time but will investigate nonlinear effects as suggested by the data. Subsequent models will contain time-varying covariates (i.e., dose of intervention, weight, exercise) and thus will focus on within-participants effects, that is, whether within-participant differences in the covariates are associated with within-participant differences in anxiety. We will examine the potential of cognitive beliefs and perceived difficulty in leading a healthy lifestyle in mediating the effects of the COPE-P program on healthy lifestyle behaviors and psychological symptoms. Rather than detecting mediated effects with the causal steps approach of Baron and Kenny, we will use the Joint Significance Test established by MacKinnon, which assesses the statistical significance of the X to M relation,  $\alpha$  path, and then the M to Y relation,  $\beta$  path. If both are statistically significant, there is evidence of mediation. Models with more than one mediator are simply extensions of the single-mediator case. In our multilevel models, we will investigate mediation effects within the different levels of analysis and across levels. Finally, we will explore characteristics that may moderate healthy lifestyle behaviors, psychosocial health, and birth outcomes (e.g., race/ethnicity, age, parity, language spoken, level of education, income, marital status) in the above models. The proposed examination of mediators and moderators should allow for increased understanding of mechanisms underlying any intervention effect and different responses among the participants. The most appropriate covariance structure for the residuals  $\epsilon_{ij}$  will be determined after data collection and the correlation of responses over time is estimated. Several covariance structures will be examined and the resulting models compared for fit using the quasi-likelihood independence model information criterion (QIC) fit using SAS 9.4 (Proc MIXED).

Should any of the outcomes need to be dichotomized (i.e., present vs. absent), we will fit a multi-level random effects logistic regression models with time-varying covariates. The basic model, to which we will add our controls and predictors, can be written: where  $i$  indexes participants,  $t$  indexes time, COPE-P is an indicator of the intervention group, COPE-P x Time is the intervention by time interaction,  $X_k$  is a set of time-varying covariates measured for each participant  $i$  at time  $t$  and  $u_i$  is participant-specific error term. The interaction term COPE-P x Time is the test of the effectiveness of the COPE-P program. If successful, the regression coefficient will be negative, indicating that the modeled probability of psychological symptoms declined more

07/30/2021

rapidly with time in the COPE-P group than they did in the PregnancyPlus group. We will fit these models using SAS 9.4 (Proc NLMIXED).

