## Research Protocol: Healthy Lifestyle Prenatal Care Study

### Aims:

**Specific Aim 1.** Use a RCT to evaluate the short- and more long-term efficacy of the COPE-P program to improve healthy lifestyle behaviors (nutrition and exercise), psychosocial health, and birth and post-natal outcomes in pregnant emotionally distressed minority women as compared to an attention control group.

**Hypotheses 1a (primary outcomes).** Immediately after the COPE-P program, at 4-6 weeks postpartum (3 months post intervention), and at 6 months postpartum (8 months post intervention), COPE-P participants will report higher healthy lifestyle behaviors, and less anxiety, stress and depressive symptoms than will the attention control participants.

**Hypothesis 1b (secondary outcomes).** COPE-P participants will demonstrate more appropriate pregnancy weight gain, better birth outcomes (mode of delivery, birth weight, and gestational age), more appropriate postpartum weight loss, and better breastfeeding outcomes than attention control participants.

**Specific Aim 2.** Examine the role of cognitive beliefs and perceived difficulty in leading a healthy lifestyle in mediating the effects of the COPE-P program on healthy lifestyle behaviors and psychological symptoms in minority pregnant women.

**Hypothesis 2 (theory building exploratory).** The effects of the COPE-P program on participants' healthy lifestyle behaviors and levels of anxiety, stress and depressive symptoms will be mediated by beliefs about their ability to make healthy lifestyles choices and their perceived difficulty in leading a healthy lifestyle.

**Exploratory Aim.** Explore characteristics that may moderate healthy lifestyle behaviors, psychosocial health, and birth and post-natal outcomes (e.g., race/ethnicity, income, age, parity, language, level of education, marital status).

**Research Question:** What is the short and long-term effect of the COPE-P program in high-risk pregnant minority women receiving prenatal care on healthy lifestyle behaviors (nutrition and exercise), psychosocial health (healthy lifestyle beliefs, healthy lifestyle behaviors, anxiety, stress and depression), and birth and post-natal outcomes (gestational age at birth, gender, birth weight, birth length, overall health, mode of delivery, breastfeeding (initiation and duration) versus an attention control group (PregnancyPlus group).

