At eight months post intervention (**T3** - six months postpartum at the six-month well baby visit), all women will once again be contacted and complete all measures (including weights taken on available pediatric clinic adult scales –same model as prenatal scales). Participants will receive \$50.00 for their participation. Outcome data from charts will be collected by team members blind to group assignment.

If study visits cannot be conducted face-to-face, data will be collected through telehealth methods such as via phone or video call (Zoom or Facetime etc.).

**Sampling.** Women will be recruited from the antenatal clinic if they are: between 18 and 40 years old, in their first trimester with an uncomplicated singleton pregnancy of less than 19 weeks, and self-identify as either Black or Hispanic and can read and speak English or Spanish. A completed sample size of 182 Black and Hispanic women from JMC in the Bronx and 182 Black and Hispanic women from OSU Total Health and Wellness clinics will be required to meet the determined sample size of 364 total (at 4 data collection points for each, resulting in ~1,450 observations). This will have greater than 80% power to detect small to moderate effects (i.e. 25 or greater) between group differences in healthy lifestyle behaviors, psychosocial health, and outcomes testing at alpha = .05 for all proposed models. The sample of 364 will have > .80 to detect a small to medium mediated effect. The sample of 364 will have > .80 to detect a small to medium mediated effect.

**Setting. Jacobi Medical Center** is part of New York City Health + Hospitals (NYC H + H), the largest municipal hospital system in the United States. New York City Health + Hospitals oversees the public health care system in all the five boroughs that comprise New York City. It provides one-fifth of the total number of discharges and more than one-third of the emergency services and hospital-based clinic visits in all of New York City. Jacobi Medical Center is an academic affiliate of the Albert Einstein College of Medicine. Jacobi Medical Center is located in the Bronx. As one of the largest health care delivery facilities in the Bronx and in New York City, Jacobi Medical Center has developed a world- wide reputation of distinction. It is renowned for its primacy in

07/30/2021

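### The readable text names no confirmatory analysis for the four primary outcomes and gives no success or multiplicity rule for them

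*Combined protocol and SAP*

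**What the plan says.** - **Hypotheses 1a (Aims).** COPE-P is predicted to do better on healthy lifestyle behaviors, anxiety, stress and depressive symptoms: "Immediately after the COPE-P program, at 4-6 weeks postpartum (3 months post intervention), and at 6 months postpartum (8 months post intervention"). No outcome or visit is ranked first.
- **Sampling.** More than 80% power is claimed with 364 completers for an effect printed as 25 or greater, with "outcomes testing at alpha = .05 for all proposed models".
- **Analysis plan, preliminary analyses.** "Analysis will begin with characterization of the sample with descriptive statistics". Baseline and attrition differences, data screening and psychometrics follow. No between-arm outcome test, visit or threshold is listed.
- **Analysis plan, hypothesis-driven analyses.** An open list of tests, from t-tests and correlations to repeated-measures ANCOVA, is applied "for each significant outcome in the preliminary bivariate analyses, (primary outcomes are healthy lifestyle behaviors, anxiety, stress, and depressive symptoms"). Growth models are assigned to the secondary outcomes.
- **Analysis plan, continuous outcomes.** "For all continuous outcomes, such as anxiety, the basic model, to which we can add our controls and predictors". Level 2 relates intervention group to "initial anxiety level and rate of change in anxiety". On time: "We will begin with a linear model for time but will investigate nonlinear effects as suggested by the data".
- **Analysis plan, dichotomized outcomes.** "The interaction term COPE-P x Time is the test of the effectiveness of the COPE-P program". This model is used only if an outcome has to be dichotomized.

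**The concern.** Three things are left open.

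1. **Which test decides.** The primary outcomes are covered by two routes, the listed bivariate, ANCOVA and repeated-measures tests and the growth model. Neither is named as the one that counts.
2. **Whether testing is conditional.** The first route appears to depend on a preliminary significance result that is not defined. The second has no such condition.
3. **What counts as success.** Hypothesis 1a joins four outcomes over three visits. Nothing says whether one, some or all must be significant, or how alpha is shared.

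The analyst could therefore settle the deciding test and the meaning of a positive trial after seeing results, while still following the plan. An arm-by-time slope also asks a different question from Hypothesis 1a, which predicts arm differences at each visit.

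**Working it through.** **Inputs from the documents.** Four primary outcomes; three post-baseline visits (T1, T2, T3); alpha .05; 364 completers (Sampling); two intervention and two control groups per segment (Overview of the design), hence 364/2 = 182 per arm.

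**Assumptions.** Two-sided tests. The printed 25 is read as d = 0.25 SD. Correlation between any two visits, baseline included, is .3/.5/.7. Outcome correlation is .3 to .7. No clustering unless stated.

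**1. The plan's own power figure.** For a single visit, unadjusted, z = 0.25/√(2/182) = 0.25/0.1048 = 2.385, so power = Φ(2.385 − 1.960) = 66.5%. The baseline-adjusted T1-T3 average gives 95-99% (step 4). Reading 25 as Cohen's f (d = 0.5) gives over 99% for a single visit. Whether more than 80% is reached depends on a test and an effect metric that the plan does not name. The observation count does agree: 364 × 4 = 1,456, against about 1,450 stated.

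**2. The two routes side by side.**

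| | Listed tests | Growth model |
|---|---|---|
| Applies to | Outcomes significant in a preliminary step (plain reading) | All continuous outcomes |
| Method | Open list | Multilevel model; linear time first, then as the data suggest |
| Arm effect | Not specified | Initial level and rate of change |
| Named confirmatory | No | No |

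The one term called the test of effectiveness belongs to the model for dichotomized outcomes. The primary outcomes are described as scale scores.

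**3. Familywise error when any one significant result supports a claim.**

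- Four independent tests: 1 − 0.95⁴ = 18.5%. Simulated with outcome correlation .3 to .7: 17.4% to 13.0%.
- Twelve independent tests: 1 − 0.95¹² = 46.0%. With outcome correlation .3 to .7, and test statistics at different visits correlated about .2 to .7: roughly 43% to 27%.
- All four required, no outcome having an effect: at most 0.6%.

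**4. Do the candidate tests agree?** Take a constant effect of 0.25 at T1-T3.

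- *Linear slope, visit index 0-3.* Weights (−1.5, −0.5, 0.5, 1.5)/5. Expected difference = 0.25 × (−0.5 + 0.5 + 1.5)/5 = 0.075. Variance per woman = 0.2(1 − ρ). At ρ = .3, SE = √(2 × 0.14/182) = 0.0392, z = 1.912, power 48%.
- *Baseline-adjusted average of T1-T3.* Variance per woman = (1 + 2ρ)/3 − ρ². At ρ = .3 this is 0.4433, SE = √(2 × 0.4433/182) = 0.0698, z = 3.582, power 95%.

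| ρ | Slope, .05 | Average, .05 | Average, .0125 |
|---|---|---|---|
| .3 | 48% | 95% | 86% |
| .5 | 62% | 96% | 88% |
| .7 | 83% | 99% | 96% |

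With no true effect, the two statistics correlate .53/.61/.68. Reporting whichever is significant gives about 8.5-9% error for a single outcome.

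**The case against.** **The listed-tests sentence is garbled.** This stands. The tests in it are themselves called bivariate, so the condition may refer to that same step. A reader might infer that some primary outcomes will never be tested, or that the condition biases the estimates. The documents do not support either. The growth model covers all continuous outcomes regardless, and any harm depends on a preliminary test that is not described. If the condition were a separate same-visit t-test, it would lower familywise error for four tests (5.0-12.9% against 13.0-17.5%).

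**The growth-model equation is missing.** It may contain an explicit arm-by-time term, so the point is limited to the readable text. Such a term would still not say which route governs, or supply a success rule.

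**The plan wants trajectories.** It does say that group differences over time must be mapped, so arm-by-time is a legitimate aim. A reader might infer that the plan could hardly detect an effect that fades. That holds only if time stays strictly linear, and nonlinear time is allowed. For effects of .25/.15/.05, a categorical arm-by-time test has 42/57/81% power against 58/60/73% for the average. Nor is the average always stronger: for an effect growing to .25 at T3, the slope has 57/71/90% and the average 67/69/82%.

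**More outcomes might count.** Aim 1 puts nutrition and exercise in parentheses after healthy lifestyle behaviors, so a reader might add diet recall and step counts to the primary tests. Measures defines that outcome by the Healthy Lifestyle Behaviors Scale, and Table 1 lists nutrition and exercise on separate rows. Four is the supported count.

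**The wording of Hypothesis 1a implies that all four must succeed.** If so, there is no inflation. The plan does not say it, and the power statement does not address it.

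**Conclusion.** The concern holds in this form: two overlapping routes to the primary outcomes, neither called confirmatory in the readable text, and no success or multiplicity rule. That conclusion rests on the text and on none of the assumed correlations.

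The size is conditional. Familywise error is about 13-17% (four tests) or roughly 27-43% (twelve) only if any single result can support a claim, and it depends on the assumed correlations. The power gap between slope and average is 48/62/83% against 95/96/99% under a constant effect, d = 0.25, 182 per arm and no clustering. It shows that the choice of test can change the answer, not that either test is wrong. The significance condition calls for deletion or clarification; it is not evidence of established harm. This should be corrected before analysis. Confidence is medium because of the garbled sentence and the missing equations.

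**What to change.** Make these edits together, because removing the condition alone could raise type I error.

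1. Delete the significance condition from the hypothesis-driven analyses.
2. Name one baseline-adjusted longitudinal model for all four primary outcomes, with visit as a category fixed in advance, reported whatever the preliminary results show.
3. Name one primary arm contrast per outcome, for example the T1-T3 average. Report the arm difference at each of T1, T2 and T3 from the same model, so that the short- and longer-term parts of Hypothesis 1a are still addressed. Label these, the trajectory analyses and the bivariate tests as supporting.
4. State the success rule: Holm across the four outcomes if any one can support a claim, or each at .05 if all four are required.
5. Restate the power in Sampling for that contrast and rule. Data management also mentions interim analyses without an alpha rule. Say whether they test primary outcomes, because Holm at the final analysis does not cover them.

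**Cost.** No new data. Holm's strictest step (.05/4 = .0125) has 86/88/96% power for the average, against 95/96/99% at .05. This is not a floor:

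- Six women per prenatal group and assumed ICC .02/.05/.10 (design effect 1 + 5 × ICC): 82/76/67% at ρ = .3.
- 165 per arm (236 × 0.7 = 165 completers per site, if both sites match): 82/85/94%.
- Assumed baseline correlation .3 and follow-up correlation .6: variance (1 + 1.2)/3 − 0.09 = 0.643, giving 84% at .05 and 68% at .0125.

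Requiring all four needs no alpha adjustment, but power for the average is then 83-97%. With an average as the primary contrast, separate confirmatory claims at each visit are given up.

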**Table 1. Study Variables, Measures and Timing**

Variables	Measures	Timing
Demographic Characteristics Age, Height Education Level, Relationship Status, Race/Ethnicity, Language Spoken, Income, Parity, Medications, Mental Health Referral/Rx post screening	Demographic and Personal Information (DPI) Form	T0 =Baseline (screening visit) T1 = 31 weeks T2 = 6-8 weeks postpartum visit T3 =6 months well baby visit
Healthy Lifestyle Behaviors	Healthy Lifestyle Behaviors Scale 	T0, T1, T2, T3
Healthy Lifestyle Beliefs	Healthy Lifestyle Beliefs Scale 	T0, T1, T2, T3
Nutrition	24 Hour Nutrition Log/Food Processor	T0, T1, T2, T3
Weight Gain/Loss, BMI	Scale	T0, T1, T2, T3
Exercise	Steps Fitbit Flex 2 Accelerometer	T0 (given at screening T1, T2, T3)
Psychosocial Health		
Anxiety	GAD7	T0, T1, T2, T3
Depressive Symptoms	EPDS	T0, T1, T2, T3
Perceived Stress	PSS	T0, T1, T2, T3
Birth and Post-Natal Outcomes	Infant Data Form	
Gestational Age at birth, Gender	Chart review	Post delivery
Birth Weight, Birth Length, Overall Health	Chart review	Post delivery
Mode of Delivery (C/S, Vaginal, Forceps/Vacuum)	Chart review	Post delivery
Breastfeeding (initiation and duration)	DPI Form	T2, T3
COPE-P Acceptability	Index (COPE-P group)	T1 and T2
Group Prenatal Care Acceptability	Group Prenatal Care Acceptability	T1
Program Experience	COPE-P/PregnancyPlus Program Evaluation	T1 and T3

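### Breastfeeding duration, a named secondary outcome seen only to 6 months, is assigned to a growth model that does not fit one duration per woman and has no rule for women still breastfeeding at T3 or lost after T2

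*Combined protocol and SAP*

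**What the plan says.** Duration is named in two places. The research question under Aims compares "breastfeeding (initiation and duration) versus an attention control group", and Table 1 lists "Breastfeeding (initiation and duration") as a Demographic and Personal Information (DPI) form item at T2 and T3. Hypothesis 1b is broader and expects "better breastfeeding outcomes than attention control participants".

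On follow-up, the Procedure section says that T3 "will be the final data collection point and will occur at a routinely scheduled 6 month well baby visit". The Overview of the design allows for 30% attrition.

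On method, the Analysis plan lists the secondary outcomes and assigns them to growth models: "postpartum weight loss and breastfeeding practices) we will fit a series of longitudinal multilevel growth models to the data". Three general provisions might also bear on the outcome:

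- a multilevel logistic model, introduced by "Should any of the outcomes need to be dichotomized (i.e., present vs. absent");
- a fallback: "Appropriate nonparametric analyses will be considered in situations of irresolvable heterogeneity";
- a missing-data rule: "Missing data will be imputed, when appropriate, using multiple imputation in SAS v9.4 PROC MI".

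Nothing in the document mentions censoring, a time-to-event method, a restricted mean, or the coding of a woman still breastfeeding at her last contact.

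**The concern.** For a woman still breastfeeding at T3, the data show only that her duration exceeds about 6 months. For a woman lost after T2 while breastfeeding, they show only that it exceeds her age-of-infant at T2. These durations are partly observed: a lower bound is known and the end is not. The assigned model has no place for such a value, so the analyst would have to settle the coding after the data are in.

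That choice matters because the women with unfinished durations at T3 are the longest breastfeeders. If COPE-P prolongs breastfeeding, there will be more of them in the COPE-P arm. Dropping them removes the women in whom the intervention succeeded. Treating their stopping time as an ordinary missing value can produce imputed durations below 6 months, which contradict what was observed, or durations above 6 months, which rest on extrapolation alone.

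**Working it through.** **Does the assigned model fit?** The growth model is described as estimating a starting level and a rate of change for each woman over four data collection periods, with random intercepts and time trends. Duration is one value per woman and has no T0 or T1 value. Modelling breastfeeding status at T2 and T3 does not rescue it. On a continuous scale, two occasions supply 2 variances and 1 covariance, or 3 quantities. Random intercept variance, random slope variance, their covariance and a residual variance are 4 parameters.

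**Does the logistic route fill the gap?** It is conditional on an outcome needing to be dichotomised, and the only outcome its text describes is psychological symptoms. Its test of effectiveness is the COPE-P by time interaction. With status seen only at T2 and T3, that tests whether the arm difference changes between the two visits. A benefit present at T2 and held to T3 on the log-odds scale gives an interaction of zero. It does not estimate duration.

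**Is there a planned figure to reproduce?** Not for breastfeeding. The general claim is over 80% power with 364 women; its effect size is read here as 0.25 standard deviations. For one value per woman with 182 per arm (364/2), 0.25/√(2/182) = 2.385, and 2.385 − 1.960 = 0.425, which gives 66.5% power two-sided. Repeated measures can raise this, but duration is not repeated.

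**How much does the coding matter?** The only input from the document is the 6-month horizon. Assumed: exponential durations, every woman initiates, control median 4 months, hazard ratio of stopping 0.75, all women followed to T3.

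- Stopping rates per month: λ0 = ln 2 / 4 = 0.1733; λ1 = 0.75 × 0.1733 = 0.1300.
- Still breastfeeding at 6 months, exp(−6λ): 35% control, 46% COPE-P.
- Mean duration restricted to 6 months, (1 − exp(−6λ))/λ: 3.73 and 4.17 months; difference 0.44.
- Mean among women who stopped by 6 months, 1/λ − 6·exp(−6λ)/(1 − exp(−6λ)): 2.49 and 2.61 months; difference 0.12.

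Dropping the women still breastfeeding therefore leaves a little over a quarter of the restricted mean difference.

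The table varies the control median. Power comes from 3,000 simulated trials with 182 per arm and a two-sided 5% test, without clustering or attrition.

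| Control median (months) | Still breastfeeding at 6 months, control / COPE-P | Restricted mean difference (months) | Difference if dropped (months) | Log-rank power | t-test power, capped at 6 | t-test power, dropped |
|---|---|---|---|---|---|---|
| 2 | 13% / 21% | 0.51 | 0.22 | 70% | 67% | 23% |
| 4 | 35% / 46% | 0.44 | 0.12 | 55% | 48% | 9% |
| 6 | 50% / 59% | 0.35 | 0.09 | 46% | 38% | 7% |
| 9 | 63% / 71% | 0.27 | 0.06 | 34% | 28% | 6% |

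The log-rank test gains 3, 7, 8 and 6 points over capping, and far more over dropping.

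**Non-initiators.** If only 80% initiate, equally in both arms, and the rest count as duration zero, log-rank power at the 4-month median falls from 55% to 35%. Comparing the proportions still breastfeeding at 6 months gives 52% and 41% in the same two settings. The rule for non-initiators needs stating in advance.

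**The case against.** The strongest objection is that the plan never says these women will be capped, dropped or imputed. Imputation is limited to cases where it is appropriate, and the sentence on growth models speaks of breastfeeding practices, which is wider than duration. Breastfeeding yes or no at T3 is fully observed for every woman seen then, and the logistic provision could accommodate it. All of that is true. It means the harm is conditional. It does not supply an analysis of duration, which remains a named outcome without a workable method.

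A second objection is that capping is harmless. For mean duration up to 6 months it is, provided every woman reaches T3: the capped difference and the restricted mean difference are then the same 0.44 months. With losses after T2 it is not, because the lost woman's time is cut at her last contact. The size of that error cannot be computed, since the share of the 30% attrition falling after T2 is not given. The power gain over capping is modest.

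A reader might go further and infer that the plan shrinks the arm difference, measured against mean duration over all time. The documents do not support that. They fix no coding. The all-time mean lies beyond any follow-up, so a censored analysis to 6 months could not recover it either. The direction also depends on the shape of the effect. With a control median of 4 months and a hazard ratio of 0.6 to month 3, 1.4 from months 3 to 6 and 1 thereafter, the capped and all-time differences are both 0.41 months. With 1.6 in place of 1.4, the capped difference (0.34) exceeds the all-time one (0.14).

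**Conclusion.** The point holds as a gap in the plan: the assigned model is unsuitable for duration, and nothing covers censoring at T3 or at loss after T2. The size of any bias depends on a coding choice that the plan leaves open. Dropping women still breastfeeding is the damaging choice: at control medians of 2 to 9 months, restricted mean differences of 0.51 to 0.27 months become 0.22 to 0.06, and power falls to between 23% and 6%. Bias from unconstrained imputation is possible but was not quantified. These figures rest on assumed exponential durations, a constant hazard ratio of 0.75, universal initiation and no clustering. They illustrate the risk and do not predict this trial's result. Duration is one part of a secondary outcome, so the primary conclusions are unaffected. The change should still be made, because it is cheap and removes a decision that could otherwise be taken after seeing the data.

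**What to change.** Take duration out of the growth-model list and define it as breastfeeding duration up to 6 months. Then specify:

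- **Analysis:** time from birth to stopping, censored at T3 or last contact if earlier, with Kaplan-Meier curves by arm and either a hazard ratio or a restricted mean difference to 6 months, chosen in advance. This assumes that loss after T2 is unrelated to stopping, which should be stated.
- **Non-initiators:** either count them as duration zero, or analyse them separately under initiation; fix the choice now.
- **Standard errors:** allow for the prenatal-care groups, since whole groups are randomised.
- **Imputation:** none for stopping times beyond T3.
- **Data:** use the infant's age at stopping from the T2 and T3 forms. The DPI form is not in the document; if it lacks this item, one question is needed.
- **Timing of T2:** Table 1 gives 6-8 weeks postpartum and the text gives 4-6 weeks. These should be reconciled, because T2 is the censoring time for women lost after it.

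The cost is analysis-plan wording and at most one form item. The downside is a narrower claim, limited to the first 6 months.
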